6.5 Dose Modification

Not applicable.

6.6 Continued Access to Study Intervention After the End of the Study

Not applicable.

6.7 Treatment of Overdose

Since the study intervention is administered by a health care professional, it is unlikely that overdose by injection occurs.

However, in the event of an overdose, the investigator should:

- 1) Contact the RMO immediately.
- 2) Evaluate the participant to determine, in consultation with the RMO, whether study intervention should be interrupted
- 3) Closely monitor the participant for any AE/SAE.
- 4) Document the quantity of the excess of the overdose in the source documents.

6.8 Concomitant Therapy

Reportable medications include medications that may affect the interpretation of safety data (eg, an antipyretic or analgesic that could have reduced the intensity or frequency of an adverse event) or may interfere with the development or measurement of the immune response (eg, the use of immune-suppressors, immune-modulators, or some antibiotics that can affect certain bioassays). Some medications such as steroids can affect both the evaluation of the safety and the immune response to a vaccine.

This may include medications of interest that were started prior to the day of vaccination, and even stopped prior to enrollment if there is a reasonable possibility that they may have an impact on safety and/or immune assessment during study participation.

The following reportable medications are defined:

- Medications impacting or that may have an impact on the evaluation of the safety (eg, antipyretics, analgesics, and non-steroidal anti-inflammatory drugs, systemic steroids/corticosteroids)
 - Note: Topical analgesics should NOT be applied at the injection site of study intervention; however, if they are applied inadvertently, they should be recorded.
- Medications impacting or that may have an impact on the immune response (eg, other vaccines, blood products, antibiotic classes that may interfere with bioassays used by Sanofi Pasteur laboratory or other testing laboratories, systemic steroids/corticosteroids, immune-suppressors, immune-modulators with immunosuppressive properties, antiproliferative drugs such as DNA synthesis inhibitors)
- Medications impacting or that may have an impact on both the safety and the immune response (eg, systemic steroids/corticosteroids)

Reportable medications will be collected in the CRF until the end of the solicited and unsolicited follow-up period.

Dosage and administration route, homeopathic medication, topical and inhaled steroids, as well as topical, ophthalmic, and ear treatments will not be recorded (except topical analgesics applied at the injection site of study intervention).

Medications given in response to an AE will be captured in the "Action Taken" section of the AE CRF only. No details will be recorded in the concomitant medication Form of the CRF unless the medication(s) received belongs to one of the pre-listed categories. Medications will be coded.

6.8.1 Rescue Medicine

Appropriate medical equipment and emergency medications, including epinephrine (1:1000), must be available at the study site in the event of an anaphylactic, vasovagal, or other immediate allergic reaction.

7 Discontinuation of Study Intervention and Participant Discontinuation/Withdrawal

7.1 Discontinuation of Study Intervention

Not applicable as there is only one vaccination.

7.2 Participant Discontinuation/Withdrawal from the Study

- A participant may withdraw from the study at any time at his/her own request or may be withdrawn at any time at the discretion of the investigator for safety, behavioral, or compliance reasons. This is expected to be uncommon.
- The reason for withdrawal should be clearly documented in the source documents and in the CRF: Adverse Event, Lost to Follow-up, Protocol Deviation, or Withdrawal by Participant or Parent / Legally Acceptable Representative.
- The participant will be permanently discontinued both from the study intervention and from the study at that time.
- If the participant withdraws consent for disclosure of future information, the Sponsor may retain and continue to use any data collected before such a withdrawal of consent.
- If a participant withdraws consent, he/she may request destruction of any biological samples taken (unless local law requires not to destroy them), and the investigator must document this in the site study records.
- Withdrawn participants will not be replaced.

Follow-up of Discontinuations

For participants who have prematurely terminated the study, the site should attempt to contact them and complete all scheduled safety follow-ups, except if they specified that they do not want to be contacted again and it is documented in the source document.

For participants where the reason for early termination is lost to follow-up, the site will not attempt to obtain further safety information. See Section 7.3 for definition of "lost to follow-up".

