2.3.1 Risks from Study Participation

The potential risks of clinical significance and risk management are summarized in Table 2.1.

Table 2.1: Potential risks of clinical significance and risk management

Potential Risk of Clinical Significance	Summary of Data/Rationale for Risk	Risk Management	
Investigated Vaccine	Investigated Vaccine: Quadrivalent Recombinant Influenza Vaccine (RIV4)		
Anaphylaxis	Anaphylaxis is an identified risk for RIV4 (see Investigator's Brochure [IB] (21) for more information regarding the data from previous experience with RIV4). No case of anaphylaxis was reported as related to trivalent recombinant influenza vaccine (RIV3) or RIV4 during the clinical development. Adverse events (immune system disorders) have been spontaneously reported during post-approval use of RIV3 or RIV4. Post-marketing observational study of safety comparing RIV3 with licensed inactivated influenza vaccine (IIV) in adults using adjusted logistic regression	Exclusion criterion E02 for those at increased risk. Observation period after vaccination for early detection and treatment. Addressed in IB (21) (administration precautions, potential adverse events). Each site must have measures to treat anaphylaxis available at the time of vaccination	

Potential Risk of Clinical Summary of Data/Rationale for Risk		Risk Management	
	analyses, showed that there was no significant difference in acute hypersensitivity reactions and fever during post-vaccination days 0-2 in the outpatient, emergency department and inpatient settings (22).		
	Background incidence rate:		
	Using health care data from the Vaccine Safety Datalink, the rate of anaphylaxis was estimated to 1.31 (95% confidence interval [CI]: 0.90-1.84) per million vaccine doses (23).		
Guillain-Barré Syndrome (GBS)	No cases of GBS were reported as related to RIV3 or RIV4	Exclusion criterion E07 for those at increased risk.	
	during the vaccine's clinical development.	During the informed consent	
	Two cases of GBS were reported during the post-marketing experience for RIV4.	process, the participants and/or their parent(s)/legally acceptabl representative(s) will be informed of this potential risk	
	A causal association between these cases of GBS and RIV4 has not been established.	and the need to attend the clinic if they are unwell. GBS is an AESI and will be collected until study end.	
		Addressed in IB (21) (administration precautions, potential adverse events)	

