7.3 Lost to Follow-up

A participant will be considered lost to follow-up if he or she repeatedly fails to return for scheduled visits and is unable to be contacted by the study site.

The following actions must be taken if a participant fails to return to the site for a required study visit or cannot be contacted as planned in the SoA:

- The site must attempt to contact the participant and reschedule the missed visit as soon as possible and counsel the participant on the importance of maintaining the assigned visit schedule and ascertain whether or not the participant wishes to and/or should continue in the study.
- Before a participant is deemed lost to follow-up, the investigator or designee must make
 every effort to regain contact with the participant (where possible, 3 telephone calls and,
 if necessary, a certified letter to the participant's last known mailing address or local
 equivalent methods). These contact attempts should be documented in the participant's
 medical record.
- Should the participant continue to be unreachable, he/she will be considered lost to follow-up.
- Site personnel, or an independent third party, will attempt to collect the vital status of the participant within legal and ethical boundaries for all participants randomized, including those who did not get study intervention. Public sources may be searched for vital status information. If vital status is determined as deceased, this will be documented and the participant will not be considered lost to follow-up. Sponsor personnel will not be involved in any attempts to collect vital status information.

Discontinuation of specific sites or of the study as a whole are handled as part of Appendix 10.1.

8 Study Assessments and Procedures

- Study procedures and their timing are summarized in the SoA. Protocol waivers or exemptions are not allowed.
- Immediate safety concerns should be discussed with the Sponsor immediately upon occurrence or awareness to determine if the participant should continue or discontinue study intervention.
- Adherence to the study design requirements, including those specified in the SoA, is essential and required for study conduct.
- All screening evaluations must be completed and reviewed to confirm that potential participants meet all eligibility criteria. The investigator will maintain a screening log to record details of all participants screened and to confirm eligibility or record reasons for screening failure, as applicable.

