An unsolicited AE is an observed AE that does not fulfill the conditions of solicited reactions, ie, pre-listed in the CRF in terms of diagnosis and onset window post-vaccination. For example, varicella or a solicited term such as headache starting after the solicited observation period (eg, headache starting on Day 10 post-vaccination in the case where headache occurring between the day of vaccination and the next 7 days is pre-listed in the protocol and CRF as a solicited reaction).

An unsolicited AR is an unsolicited AE that is considered related to an IMP.

Unsolicited AEs includes both serious (SAEs) and non-serious unsolicited AEs.

All unsolicited AEs occurring at and around the IMP injection/administration site are to be considered by default as related to the IMP administered at that site and are therefore referred as unsolicited injection/administration site ARs.

All unsolicited AEs which are not at and around the IMP injection/administration site, are referred as systemic unsolicited AE. For each unsolicited systemic AE, the investigator assesses the relationship to the IMP. Systemic AEs assessed as related to IMP are referred as systemic ARs.

Adverse Event of Special Interest (AESI):

An adverse event of special interest (serious or non-serious) is one of scientific and medical concern specific to the Sponsor's study intervention or program, for which ongoing monitoring and rapid communication by the investigator to the Sponsor can be appropriate. Such an event might warrant further investigation in order to characterize and understand it. Depending on the nature of the event, rapid communication by the study Sponsor to other parties (eg, regulators) might also be warranted.

Medically Attended AE (MAAE):

An MAAE is a new onset or a worsening of a condition that prompts the participant or participant's parent/legally acceptable representative to seek unplanned medical advice at a physician's office or Emergency Department. Physician contact made over the phone or by email will be considered a physician office visit for the purpose of MAAE collection. This includes medical advice seeking during the study visit or routine medical care. This definition excludes pediatric check-ups, follow-up visits of chronic conditions with an onset prior to entry in the study, and solicited reactions.

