3.4.3 Secondary Endpoints

Immunogenicity

success.

The immunogenicity parameters will be calculated with their 95% CIs using the exact binomial distribution (Clopper-Pearson method) for proportions and using normal approximation of log-transformed for GMTs and GMTs ratio. The 95% CI of proportions difference (ie, difference between vaccine groups in SC) will be calculated using Wilson Score method without continuity correction. All analyses will be conducted by study group.

The following descriptive statistics will be displayed:

- GMTs of individual-HAI titer on D01 and 28 days after vaccination (D29)
- Percentage of participants with detectable HAI titer, ie, with a titer ≥ 10 (1/dil) at D01 and 28 days after vaccination (D29)
- GMs of individual titer ratio: 28 days after vaccination (D29) /D01
- Percentage of participants with titer ≥ 40 (1/dil) on D01 and 28 days after vaccination (D29)
- SC rates (titer < 10 [1/dil] at D01 and post-injection titer ≥ 40 (1/dil) at D29 or titer ≥ 10 (1/dil) at D01 and a ≥ 4-fold rise in titer (1/dil) at D29)
- The RCDCs of pre-vaccination titer (D01), and post-vaccination titer (D29) will be generated for each study group. The RCDCs will include the plots of the 2 study groups the same figure.

The analysis will be conducted for each immunogenicity variable on the PPAS, and on FAS if the attrition rate from FAS to PPAS is greater than 10%.

In addition, subgroup analyses will be performed; in particular, immunogenicity will be described according to age subgroups (9-11y, 12-17y, 18-34y and 35-49y), sex, race, previous influenza vaccination status (received a seasonal influenza vaccine in the last past influenza season or not) and baseline seropositivity status (seropositive and seronegative are defined as baseline antibody titer $\geq 1:10$ or < 1:10)., as appropriate according to number of participants in the respective subgroups.

Safety

For the main safety parameters, 95% CIs of point estimates will be calculated using the exact binomial method (Clopper-Pearson method) for single proportions and using the normal approximation for quantitative data.

SAP Core Body: VAP00027

All analyses will be descriptive; no hypotheses will be tested.

The number of participants with documented safety will be used as denominator of the frequencies.

For solicited reactions, the denominator will be the total number of participants who have non-missing data for the endpoint considered

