For unsolicited AEs, the denominator will be the total number of participants who were vaccinated.

SafAS will be the analysis population of safety data.

In terms of contents, solicited reactions will be presented by time to onset, maximum severity, number of days of occurrence and action taken; unsolicited AEs will be presented by causal relationship, time of onset, maximum severity and duration; SAEs will be presented by causal relationship, seriousness and outcome.

Subgroup analyses will also be performed; in particular, the main safety endpoints will be described according to age subgroups (9-11y, 12-17y, 18-34y and 35-49y), previous vaccination status, sex and race, as appropriate according to number of participants in the respective subgroups.

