4.2.1.2.6 Serious Adverse Events

An event will be considered as a serious event if "Yes" is checked for "Serious" in the CRF.

SAEs will be analyzed within 28 days after vaccination, from D29 to 180 days after vaccination, and within 180 days after vaccination.

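### Participants coded lost to follow-up get no D181 safety call, and the unsolicited-AE denominator rule still counts them in the late SAE and AESI rates

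*Protocol*

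**What the plan says.** **Follow-up.** Protocol 7.2 treats early terminators in two ways. In general: "For participants who have prematurely terminated the study, the site should attempt to contact them and complete all scheduled safety follow-ups", unless they have declined contact. For those coded lost: "For participants where the reason for early termination is lost to follow-up, the site will not attempt to obtain further safety information". Protocol 7.3 sets out the contact attempts required before that code is used and adds a further search: "Site personnel, or an independent third party, will attempt to collect the vital status of the participant within legal and ethical boundaries". The Schedule of Activities has only one contact after Visit 2 (D29), the D181 phone call. Protocol Table 2.1 says of Guillain-Barré syndrome: "GBS is an AESI and will be collected until study end".

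**Analysis.** Protocol 10.2.1: "Unsolicited AEs includes both serious (SAEs) and non-serious unsolicited AEs". The SAP likewise places SAEs and AESIs under its unsolicited-AE heading (4.2.1.2). SAP 4.2.1.2.6: "SAEs will be analyzed within 28 days after vaccination, from D29 to 180 days after vaccination, and within 180 days after vaccination"; 4.2.1.2.7 gives the same three windows for AESIs.

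**Denominator.** SAP 3.4.3, like Protocol 9.4.3, first gives a general rule: "The number of participants with documented safety will be used as denominator of the frequencies". It then gives one for solicited reactions (non-missing data for the endpoint) and one for unsolicited events: "For unsolicited AEs, the denominator will be the total number of participants who were vaccinated". No window-specific denominator and no person-time analysis is given, and SAP 3.4.5.1 generally does not replace missing safety data.

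**The concern.** The follow-up rule and the denominator rule work against each other. Being unreachable near D29 does not show that a person will be unreachable in month six, yet 7.2 ends the attempts. That person then stays in the denominator for a window in which nobody asked about events, and so is tabulated as event-free. A participant who attends Visit 2 but is not reached at D181 has the same effect, because no other contact is scheduled in between.

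SAEs and AESIs throughout the study belong to a key secondary objective, described by age group, in a trial meant to support extension to children. A reader of the six-month rates should be able to see how many participants they rest on. If the fraction not followed differs between children and adults, equal true rates would be reported as unequal.

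**Working it through.** **Inputs from the documents**
- 600 evaluable per group and about 10% attrition (Protocol 9.2, SAP 3.2).
- 667 enrolled per group, 1334 in all.
- Exact (Clopper-Pearson) 95% intervals for proportions (SAP 3.4.3).
- Visit 2 at D29 and the call at D181, so the gap is 181 − 29 = 152 days.

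**Assumption.** The documents give no loss-to-follow-up rate. I call it d and use 2% to 10%. The 10% is a ceiling: it is the plan's allowance from enrolled to evaluable, not a loss rate.

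**1. The plan's figure.** 600 / (1 − 0.10) = 666.7, so 667 per group and 1334 in total. This reproduces.

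**2. D29 to 180 days, point estimate.** Let p be the true rate, the same in lost and followed participants. Events are seen only in the followed, so the all-vaccinated rule estimates p(1 − d). The relative understatement is d: 2%, 5% and 10% at d = 2%, 5% and 10%.

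**3. The same window, upper limits per age group.** With zero events the exact limit is 1 − 0.025^(1/n).

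| Denominator | n | 0 events, upper limit | 5 events, rate (95% CI) |
|---|---|---|---|
| All vaccinated | 667 | 0.55% | 0.75% (0.24–1.74) |
| Followed, d = 2% | 654 | 0.56% | 0.76% (0.25–1.78) |
| Followed, d = 5% | 634 | 0.58% | 0.79% (0.26–1.83) |
| Followed, d = 10% | 600 | 0.61% | 0.83% (0.27–1.93) |

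The upper limit moves by 0.01 to 0.06 percentage points at zero events and by 0.03 to 0.19 points at five.

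**4. Within 180 days.** Time before loss is observed. With a constant hazard and loss at day t, the relative understatement is about d(180 − t)/180. At d = 10% this is 10% for t = 0 and 0.10 × 151/180 = 8.4% for t = 29. At d = 2% it is 2.0% to 1.7%.

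**5. Coverage of the interval.** With N = 667 and d = 10%, the all-vaccinated exact interval covers the true rate 97.5% of the time at p = 1% and 95.0% at p = 2%. The lowest value examined was 94.1% (N = 1334, p = 2%, d = 10%). The misses do become lopsided. At N = 667 and p = 2%, the upper limit falls below the true rate 4.4% of the time at d = 10%, against 2.0% with no loss.

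**6. Unequal loss, as an illustration.** With d = 2% in adults and 10% in children (assumed, from the range above), a common true rate of 1.0% would appear as 0.98% and 0.90%.

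**The case against.** The case for leaving the plan alone has several parts, and much of it stands.

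- **The lost are not simply dropped.** Section 7.3 requires every effort first: where possible three calls and, if necessary, a certified letter. Vital status is then sought, and a participant found to have died is no longer classed as lost. Protocol 8.3.1 also requires notification of any SAE the investigator learns of after discharge and considers related. So deaths are at least partly captured. Non-fatal SAEs and AESIs are not actively sought.
- **A reader might infer that 7.2 and 7.3 contradict each other.** They do not. Vital status is narrower than safety information, and a site can follow both sections.
- **A reader might take the all-vaccinated denominator as settled.** It is not: the documented-safety sentence could be read to remove people with no data after D29. But that sentence names no window, and a participant lost before D29 can have documented safety from the first 30 minutes. The text does not decide between the readings.
- **A reader might treat the 10% as early loss.** Attrition to evaluable also has to cover per-protocol exclusions (eligibility, sampling window, prohibited medication) that leave safety follow-up intact, and 7.2 expects withdrawal to be uncommon.
- **Crude incidence over all exposed is a legitimate, disclosed choice**, and SAP Table 3.1 provides for disposition and follow-up counts. That supports keeping the figure, but not leaving it without the number followed beside it.

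**Conclusion.** The point holds as a modest, correctable weakness. Under the specific denominator rule, late-window SAE and AESI rates and limits are shifted down by about the fraction not followed. That is about 2% relative at 2% loss and at most about 10% if the whole attrition allowance were loss. The 180-day rate is affected slightly less. These sizes assume that the lost have the same risk as the followed. Loss related to an event could make the shift larger, but the documents give nothing from which to size it.

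Two stronger conclusions are not supported. The confidence intervals are not invalid: coverage stays at or near 95% throughout the range examined. Nor is any conclusion of the trial at risk, because the safety analysis is descriptive and tests no hypothesis. What remains is an avoidable gap in six-month safety ascertainment and a denominator that the plan states in two ways.

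**What to change.** 1. **Protocol 7.2.** Attempt the scheduled D181 call for every vaccinated participant who has not refused contact, including those coded lost to follow-up.
2. **SAP 3.4.3, 4.2.1.2.6 and 4.2.1.2.7.** Reconcile the two denominator sentences and say which applies in each window. Report the number followed to D181 by age group. For D29 to 180 days, show the SAE and AESI rate among participants with follow-up after D29, or per person-time, beside the all-vaccinated figure.
3. **The 180-day window.** Use person-time, or the all-vaccinated figure with the number followed. Do not restrict the denominator to participants who either completed the D181 contact or had an event recorded. That selects on outcome, because it keeps lost participants with events and drops those without. For example, if all 6 SAEs among 667 occurred before any loss, 6/667 = 0.90% is the correct crude figure, whereas a denominator of 600 to 606 would give 1.00% to 0.99%.

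**Cost.** One extra call attempt per lost participant, a few table lines, and slightly wider intervals. The Schedule of Activities already has a six-month follow-up record in the CRF, from which the number followed can be counted. If the D181 contacts are already past, items 2 and 3 can still be done.
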